
not uninstall the app after the study ended, the apps will be closed and no additional information will be

used or collected through the app.

Subject Privacy

Privacy refers to the person's desire to control access of others to themselves. Privacy concerns people, whereas confidentiality concerns data. Describe the strategies to protect privacy giving consideration to the following: The degree to which privacy can be expected in the proposed research and the safeguards that will be put into place to respect those boundaries. The methods used to identify and contact potential participants. The settings in which an individual will be interacting with an investigator. The privacy guidelines developed by relevant professions, professional associations and scholarly disciplines (e.g., psychiatry, genetic counseling, oral history, anthropology, psychology).

All encounters will take place in the outpatient clinic setting, telephone, email, BlueJeans or via Way to Health, HIPAA compliant platform. To enroll provider participants, we will discuss the trial during their team meeting and provide informed consent in-person or electronically via the Way to Health platform. To enroll patient participants, we will discuss the trial via email, phone calls, or BlueJeans or on other platforms and applications outlined on the Penn Medicine / Penn Dental / UPHS (HIPAA Covered Entities) Guidance on Remote Consent Discussion and Documentation Related to COVID-19 Concerns. During the discussion, we will give them the opportunity to sign the informed consent document online or in-person. They will then complete the baseline survey, and install AWARE on their iPhone Participants can donate their digital data in-person or virtually. Regardless of the mode, patient participants will be emailed a detailed study packet noting all procedures and schedule a time (in-person or remote) to assist them to donate their data to a secure url, http://

donate.centerfordigitalhealth.upenn.edu (reviewed and approved by Penn Medicine Information Security). Patients will receive a unique Way to Health ID. Patients who choose to share their Facebook, Instagram, Google takeout or other social media data will be given a unique ID that will be linked to identifiable information. Participants who install the application to share their Facebook posts will be able to opt in and out of the application at their discretion. The Facebook application will access data that is stored in the user profiles in the Facebook platform. When participants first click on the link to use the app, they will first be greeted by the Facebook consent screen that will ask the user permission for the application to have access to their profile information and to consent to the terms and service of the application. Participants would have to agree to this screen in order to use the application. They will have to click agree to access the application. All language data will be stored on secure severe using only the unique study ID which can be used to link this data to the REDCap database. This linkage will be stored in a double locked fashion on a password protected computer will access only by the principal investigator and key study personnel. The study team will not have direct access to any participants username/password for any digital media accounts and will not have the ability to post any messages or content on behalf of the user. The study team will not communicate with participants via social media or publicly post that the participant is involved in the study. Participants will be informed that they should not have any expectation of surveillance or medical advice/medical response or that any posts, searches, physical activity data will be responded to in real time or at any time by the study team. The focus group will be instructed that there are no right or wrong answers, only differing opinions. The session will be audio-recorded and that we ask that they please speak one at a time. The discussions are being used for research and everything will remain confidential and anonymous. No responses will be connected to a participants name and if there are any questions one does not want to answer, they do not have to. We will instruct all participants that the focus groups intention to keep discussion within the group and not to share information or details once the discussion is over. Focus group audiorecordings will be transcribed verbatim and all identifiers will be removed. The recording and transcript will be kept a secure and locked area with access limited to designated researchers. After we analyze the recordings, we will destroy recordings after data analysis or completion of the study. The day 60

NCT04011540 January 6, 2022

interviews will be audio-recorded if the participant agrees, if they prefer to not be recorded, the interviewer will take notes. No digital data or social media displayed on the dashboard will be reviewed real-time.

Data Disclosure

Data responses from participants will be linked to participant identifying information, and data will be available only for listed study personnel and the IRB if requested. However, all potential subjects will be informed that the information they provide will be held in confidence to the extent that the law allows, but that the exception to this confidentiality is any disclosure of potential for immediate harm of themselves or others, such as active suicidal or homicidal ideation or child abuse. The participants will be notified prior to participation that if any of these issues are raised, the researchers will take whatever steps are necessary to protect the subject or others, including bringing risk of harm to the attention of the proper authorities. This applies only to direct verbal disclosure by the patient and not to any data included in social media data. Specifically, the research team will not review social media data to determine disclosures of suicidal, homicidal, or child abuse information that will be acted on by the research team. Data collected for analysis is detailed in the informed consent form and specifically indicates: Data extracted from Facebook will include but not be limited to past and future content: age, gender, language, photos, News Feed content, work history, education history, hometown, interests, relationship status, current city, religious or political views, number of friends, items liked, and number and status updates. Data from Instagram will include username/ handle, number of posts, engagement metrics, text captions, and messages, Google takeout includes, My Activity and YouTube, for more details, please see, https://takeout.google.com/.

Data protection

x Name x Street address, city, county, precinct, zip code, and equivalent geocodes x All elements of dates (except year) for dates directly related to an individual and all ages over 89 x Telephone and fax number x Electronic mail addresses x Social security numbers Medical record numbers Health plan ID numbers Account numbers Certificate/license numbers Vehicle identifiers and serial numbers, including license plate numbers x Device identifiers/serial numbers x Web addresses (URLs) x Internet IP addresses x Biometric identifiers, incl. finger and voice prints x Full face photographic images and any comparable images x Any other unique identifying number, characteristic, or code

Consent Process Overview

Based on the potential risks and benefits described below, we believe this study may be considered minimal risk.

Potential Study Risks

Since participation in this research project will not alter patient management in any way, we believe that there will be minimal to no risk posed to participants. The most significant risk will be breach of confidentiality. This risk is minimal given the various safeguards embedded in our data storage and management. The participants will be notified prior to participation that if any of these issues are raised, the researchers will take whatever steps are necessary to protect the subject or others, including bringing risk of harm to the attention of the proper authorities. This applies only to direct verbal disclosure by the patient and not to any data included in social media data. Specifically, the research team will not review social media data to determine disclosures of suicidal, homicidal, or child abuse information that will be acted on by the research team. Data collected for analysis is detailed in the informed consent form and specifically indicates: Data extracted from Facebook will include but not be limited to past and future content: age, gender, language, photos, News Feed content, work history, education history, hometown, interests, relationship status, current city, religious or political views, number of friends, items liked, and number and status updates. Data from Twitter will include: handle, number of followers/following, tweets, geography, time/date, profile. Data from Instagram will include username/ handle, number of posts, engagement metrics, messages, and photos. The use of REDCap will also help minimize the risk of confidentiality. Additionally, the survey items are expected to cause no to minimal emotional distress. We do not expect physical, emotional, economic, psychological or societal harms that may accrue to others not in the trial. The study is designed to minimize the risk of harm to all participants participating by providing secure surveys and direct communication access to the research team and Principal Investigator.

Potential Study Benefits

Participants in this study may benefit directly from having a social media summary dashboard in their therapy sessions; in particular it may uncover interesting trends and correlations that could improve patient-provider communication and their engagement in treatment. It could also provide additional knowledge about how they communicate and use social media platforms, these summaries may be revealing and aid healthy behavior change and/or self-management. In addition feedback on the dashboard will help us better tailor future iterations to better meet the needs of our sample, both the patient and provider.

Alternatives to Participation

Considering the context of this study, there are no alternative to participation available to the participants outside of the research context.

Data and Safety Monitoring

As noted above, the research team will immediately contact the PI and enrolled therapist via Penn Medicine email with [ENCRYPT] in the subject, high priority note, and a read receipt. Once the PI and therapist review the text message, they will determine if the participant should continue in the study. Please see SAFETY CONCERN Email / Telephone Script and the W2H safety features attached in the submission. The safety concern protocol, it consists of two emails contacting the participants behavioral health provider alerting them of these developments. If we do not receive a response, we will report our concern to clinic director immediately. Additionally, all research staff will consult the National Institute of Mental Health (NIMH) toolkit for suicide safety assessment. Any participant who requires a level of care exceeding customary outpatient services (i.e., psychiatric hospitalization or participation in a partial

hospital program), or who otherwise report or manifest thoughts or behaviors suggesting possible safety concern due to participation in the study, will be removed from the study. In addition to the safety monitoring that takes place as part of standard care, study staff will provide clinicians with notifications about patients of potential concern through a daily email. This email will be sent through the secure Penn Medicine email system. This email will be sent each morning (Monday - Friday). Patients will be told that the notification system is active only during the business week and expectations for emergency situations will be clearly set.

Original Statistical Analysis Plan – Sent to IRB

Stata, SAS, and NVivo software will be used for analyses. All data will be summarized using descriptive statistics (mean or median, standard deviation, or interguartile range for continuous variables, frequencies for categorical variables) and graphical techniques (histograms, scatterplot) as appropriate. Standard summary descriptive statistics to be used to analyze data from the survey. We will extract data from social media and wearable device platforms and aggregate to develop dashboards. Qualitative analysis using grounded theory will be applied for the focus group discussion, interviews, and openended survey questions. We will conduct an intent to treat (ITT) analysis. The ITT analysis will include all randomized patients in the groups to which they were randomly assigned, regardless of their adherence with the entry criteria, regardless of the treatment they actually received, and regardless of subsequent withdrawal from treatment or deviation from the protocol. Baseline demographic and clinical characteristics will be reported as frequency and percent for categorical variables and median and interquartile range (IQR) for continuous variables. We will compare baseline characteristics between intervention and control arms using t-tests for continuous variables and chi-squared tests for categorical variables. The goal of these comparisons will be to determine if the two arms are balanced on baseline variables after randomization. For the primary analysis, we will use linear mixed effects models to assess whether average of SF 36 scores over study follow-up differ between the two arms. We will use a random effect to account for the correlation in repeated outcome measures over time within participants. We will also account for correlation in outcome measures by therapist (as participants will be randomized within therapist), by including additional random effects to account for the nesting of patients within therapists. The primary parameter of interest will be a binary indicator for treatment arm assignment. Models will also include a variable for time of measurement. Baseline covariates that are found to be unbalanced between arms may be adjusted for in the model if they were deemed to be potential confounders a priori to adjust for potential confounding and for efficiency gain. We will use all available SF 36 scores on eligible patients from randomization through the last observation. An advantage of the linear mixed effects model is that it is robust to missing outcome measures as long as the missingness mechanism is missing at random (MAR). Patterns of missingness will be assessed carefully and multiple imputation will be used if deemed appropriate. Robust (empirical) standard errors will be used. A $p \le 0.05$ will be deemed statistically significant but emphasis will be placed on point estimates and confidence intervals. In secondary analysis, we will also include an interaction term between intervention arm and time in order to assess whether the intervention affects the slope of SF 36 scores over time. We may also consider testing interactions between intervention and sex or other important covariates to test if there are differences in the effect of intervention by pre-specified subgroups. We will use a similar approach to evaluate secondary outcomes; however, depending on the distributional form of the secondary outcome, we will use a generalized mixed effects model with the appropriate functional forms for the distribution family and link function.

Amendments to the Statistical Analysis Plan

All amendments to the original SAP were made prior to unblinding of the data analyst and prior to access to outcome data.

Based on covariate balance between the intervention arms, we amended our original statistical analysis plan. In addition, we originally anticipated enrolling 20-30 therapist participants with several patients nested within each therapist. This would have necessitated the accounting for clustering within therapist using random effects. However, we enrolled 69 therapist participants with cluster sizes that were very small, with most therapists treating 1-2 patients. Hence, as our primary analysis, we conducted an unadjusted paired t-test (rather than our originally proposed linear mixed model) to compare mean changes on our primary outcomes from baseline to 60-day. As a secondary analysis, we did conduct a linear mixed effects model exactly as proposed in the original SAP. These results were nearly identical to the unadjusted paired t-test and would not change our conclusions. In addition, we conducted a complete case analysis as our primary analysis. After assessing patterns of missingness and determining that missing at random is a plausible mechanism in this study, we conducted multiple imputation. Again, our imputed results were nearly identical to the complete case analysis with identical conclusions.

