
January 6, 2022

Overall Objectives

Our objective is to explore and evaluate how a patient-centered personalized social media summary dashboard could be used in a behavioral health therapy session to improve depressive symptoms and anxiety and if a social media dashboard improves patient and provider therapeutic alliance and engagement.

Aims

Primary Aims

Determine the impact of incorporating digital data and electronic communication dashboard in behavioral health treatment on patient reported health-related quality of life (SF-36) compared to usual care

Secondary Aims

Determine the impact of incorporating digital data and electronic communication dashboard in behavioral health treatment on patient-reported depressive (PHQ-8) and anxiety (GAD-7) symptoms compared to usual care.

Determine the impact of incorporating digital data and an electronic communication dashboard in behavioral health treatment on therapeutic alliance (WAI-SR) compared to usual care.

Determine the impact of incorporating digital data and an electronic communication dashboard in behavioral health treatment on the CIS checklist compared to usual care.

Primary Outcome Variable

Examine self-report of health-related quality of life (SF-36), specifically mental health (vitality, social functioning, role-emotional and emotional well-being) under the intervention and control conditions and the change over the study period.

Secondary Outcome Variables

Examine depression (PHQ-8), anxiety (GAD-7), and therapeutic alliance (WAI-SR) under the intervention and control conditions and the change over the study period.

Examine the therapeutic alliance (WAI-SR) and frequency digital data and electronic communication is discussed in therapy (CIS checklist) under the intervention and control conditions and the change over the study period.

Study Design

Phase Not applicable

Design

A randomized controlled trial for patients and their mental or behavioral health provider from Penn Medicine, Hall Mercer, and/or Horizon House or greater Philadelphia mental health practices and clinics to investigate the impact of incorporating digital data and electronic communication dashboard in behavioral health treatment session. Patient and provider participants will be randomized to receive the

treatment (having a digital health dashboard to be used at least two therapy sessions over a 2-month

NCT04011540

January 6, 2022

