Patient participants will be randomized after they donate digital data sources and complete baseline survey. We will use Way to Health's computer-generated algorithm to randomize patient participants in block sizes of 2, 4, and 6. Patient participants will be randomly assigned to control (usual care) or experimental group (use of digital health dashboard over the 2-month study period). Study assignments will be stored in Way to Health. The study will be single-blinded. The research team will know which participants are receiving the active medication or treatment and which are not. The participants will not be blinded to their assignment. Provider participants will be enrolled in the arm of their patient. There is possibility that provider participants are exposed to the intervention for 1 patient and usual care for another, despite this limitation, we will control for contamination in analyses. The study biostatistician will determine when to unblind the study.

Study Duration

This entire study will last approximately 2 years. Randomized controlled trial participants, both patient and providers, involvement is approximately 3 months, 90 days.

Facilities

Our team is diverse and multi-disciplinary. [name] is an Associate Vice President at Penn Medicine and an Associate Professor of Emergency Medicine at the University of Pennsylvania. She has secondary appointments in the Department of Internal Medicine and Department of Anesthesia and Critical Care. [name] is a Professor of Psychiatry at the University of Pennsylvania, where he directs the Center for Mental Health Policy and Services Research. He also is Vice-Chair for Research. He has a 30-year history of partnering with mental health providers in Philadelphia to improve care. [name] is a postdoctoral researcher and his research leverages large-scale social media image and text data to model social health outcomes and psychological traits. [name] is an Assistant Professor of Psychology in Psychiatry in the Perelman School of Medicine, University of Pennsylvania.

NCT04011540 January 6, 2022

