We will draw upon our working relationships with our various recruitment sites. The randomized controlled trial will be powered on SF-36 change in the patient participant. We used PASS to calculate the minimum detectable score difference required for over 80% power assuming a type I error rate of 0.05. We assumed 50 in each arm. We used the test for two means in a repeated measures ANCOVA. We assumed the correlation between repeated measures to be 0.60 (r2=0.36). The following values were used in the sample size calculations: SF36 Norms Mental Component Summary (MCS): mean = 50; sd = 10 Vitality: mean = 60.9; sd = 21.0 Social Functioning: mean = 83.3; sd = 22.7 Role-Emotional: mean = 81.3; sd = 33.0 Mental Health: mean = 74.7; sd = 18 Table: Minimum detectable score differences Sample Size 50 in each arm MCS 5 Vitality 10 Social Functioning 11 Role-Emotional 15 Mental Health 9 We aim to enroll 115 participants in a randomized controlled trial, with the anticipation that there will be 15% attrition.

Patient Subject Recruitment

We will identify participants across several settings: inpatient and outpatient Penn Medicine clinics (e.g., Emergency Department, Internal Medicine, Center for Cognitive Therapy, PIC, LGH mental health clinics), flyers at [name] and Penn Medicine iConnect (Use of Patient Electronic Communication in Psychiatric Evaluation and Treatment, Study Identifier: 831246), Google ads, Facebook ads, ResearchMatch.org, and provider referrals. Interested patient participants will be directly approached by a research assistant (RA) via email, telephone or BlueJeans. Patients who are receiving care in these settings will receive a digital or printed flyer about the opportunity to participate in a research study. In outpatient units, Ras or AAs will meet regularly with the nursing coordinator, office manager, charge nurse, nurse/ physician team to determine the daily census and appropriateness of approaching patients. If necessary, research assistants will also communicate directly with patients providers (physicians, residents or nurses) to determine whether it is appropriate to approach the patient.

NCT04011540 January 6, 2022

Potentially eligible patients will be approached via email, telephone or BlueJeans to verify they meet all inclusion criteria and will then be asked to participate.

Compensation

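### The amended primary analysis is called a paired t-test with no arm contrast; taken as written, it cannot compare dashboard with usual care

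*Combined protocol and SAP*

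**What the plan says.** The section Amendments to the Statistical Analysis Plan replaces the linear mixed model, as primary analysis, with an "unadjusted paired t-test (rather than our originally proposed linear mixed model) to compare mean changes on our primary outcomes from baseline to 60-day". The same name returns when the mixed model, now secondary, is compared with it: "These results were nearly identical to the unadjusted paired t-test and would not change our conclusions". Neither sentence names the arms or a between-arm difference.

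Every other statement about the primary question is between-arm:

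- **Primary Aims:** the effect of the dashboard in "behavioral health treatment on patient reported health-related quality of life (SF-36) compared to usual care".
- **Method for Assigning Subjects to Groups:** "Patient participants will be randomly assigned to control (usual care) or experimental group", with randomisation of individual patients in blocks of 2, 4 and 6.
- **Accrual:** "We used the test for two means in a repeated measures ANCOVA", with 50 per arm.
- **Analysis Plan and Original Statistical Analysis Plan:** the model is "to assess whether average of SF 36 scores over study follow-up differ between the two arms", and "The primary parameter of interest will be a binary indicator for treatment arm assignment".

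**The concern.** A paired t-test needs paired observations and tests whether their mean difference is zero. The only pairing in these documents is a patient's own baseline and day-60 score. Applied to that pairing, within one arm or over both, the test measures change over time and has no arm parameter.

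This is the primary test of record, so a reader cannot tell which hypothesis the headline p-value tests and cannot reproduce it. The distinction matters here because the inclusion criteria require all patients to be in ongoing therapy. Scores may therefore improve in both arms with no dashboard effect, and a paired test would count that improvement as a positive finding.

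**Working it through.** **1. Reproduce the plan's power figures.** Inputs from Accrual: 50 per arm, alpha 0.05 (taken as two-sided; the plan does not say), over 80% power, correlation 0.60, SDs 10 (MCS), 21.0 (Vitality), 22.7 (Social Functioning), 33.0 (Role-Emotional) and 18 (Mental Health).

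Baseline-adjusted SD = SD × √(1 − 0.60²) = 0.8 × SD. Solving a two-sample comparison for 80% power (noncentral t, 98 df) gives detectable differences of 4.53, 9.51, 10.28, 14.94 and 8.15. Rounded up, these are the stated 5, 10, 11, 15 and 9. The trial was therefore sized on a between-arm, baseline-adjusted comparison.

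**2. Inputs for comparing the tests (MCS scale).**

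- Completers: 115 × 0.85 = 97.75, about 98, or 49 per arm.
- SD of change = 10 × √(2 × (1 − 0.60)) = 8.94, applying the 0.60 to baseline versus day 60.

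**3. Literal reading: some form of paired test, no true arm effect.** The common improvement is my assumption; the documents give none. Power is exact noncentral t. With p the within-arm paired rejection rate, the chance of significance in the intervention arm but not in control is p × (1 − p). The documents state no such decision rule; it is shown because within-arm tests are often read that way.

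| Improvement in both arms | Paired, intervention arm (n = 49) | Paired, arms pooled (n = 98) | Significant in intervention arm only | Two-sample on change |
|---|---|---|---|---|
| 1 point | 12% | 20% | 10.5% | 5% |
| 2 points | 33% | 59% | 22% | 5% |
| 3 points | 63% | 91% | 23% | 5% |
| 4 points | 87% | 99% | 11.6% | 5% |

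The intervention-only figure peaks at 25%, at 2.5 points, where p = 0.483. Simulation with 40,000 trials put the two-sample test at 4.9% to 5.1%.

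The error can also run the other way. If a true 5-point arm effect arises as +2.5 versus −2.5, the pooled mean change is zero. The pooled paired test is then significant in about 4% of trials and the two-sample test in 78%.

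**4. Mislabel reading: a two-sample t-test on change.** There is no inflation of type I error. Precision at 49 per arm:

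- Two-sample on change: SE = 8.94 × √(2/49) = 1.81; 95% CI half-width 3.6; power for 5 points 78%.
- ANCOVA: SE = 8 × √(2/49) = 1.62; half-width 3.2; power for 5 points 86.5%.

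At the plan's own 50 per arm and stated differences (noncentral t), the change-score test has 71% to 79% power across the five scales, against 80% to 87% for ANCOVA.

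**The case against.** The strongest reply is that this is plainly a slip of naming. The amendment opens with "Based on covariate balance between the intervention arms, we amended our original statistical analysis plan" and goes on to an unadjusted test. Balance between arms justifies dropping adjustment only if the arms are being compared. The sentence speaks of comparing mean changes, in the plural. The mixed model, whose primary parameter is the arm indicator, is said to give nearly identical results, which would be surprising beside a pooled paired test. The second use of the name only refers back to the first. On this reading nothing needs re-running.

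Most of this stands, and a misnamed two-sample test is the likelier reading. It does not remove the fault, because the test of record is still wrong as written. Nor does the reported agreement settle which test was run: the mixed model targets average SF-36 over follow-up, the t-test targets day-60 change, and no estimates are given for either.

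It is also fair that the table in step 3 rests on assumed improvements, and that MCS appears only in Accrual, while the primary outcome lists four mental health domains. The table shows what a paired test responds to; it is not an estimate of what happened in this trial. The 5% for the two-sample test is per test and assumes independent patients. Several primary domains and therapist clustering are separate matters.

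**Conclusion.** The concern holds: the primary test as named cannot estimate the effect of the dashboard against usual care. The documents do not show that the wrong test was run.

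- **If a two-sample test on change was run:** the fault is in the description, with no inflation of type I error. For a 5-point MCS difference at 49 per arm, power is about 78%, against 86.5% for an ANCOVA of the kind used to size the trial.
- **If a within-arm or pooled paired test was run:** the primary p-value says nothing about the arm contrast. Under the assumed common improvements of 1 to 4 points it would be significant in 12% to 99% of trials with no arm effect.

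These figures rest on the plan's SD of 10, correlation of 0.60 and 15% attrition, and on a two-sided 5% test. The fault is confined to the primary test; the mixed model kept as a secondary analysis does address the aim. Correction is required because this is the trial's primary analysis.

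**What to change.** The sponsor should first state which test was run.

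- **Two-sample test on change scores:** replace the wording in both places with: an unadjusted independent two-sample t-test comparing mean change in SF-36 from baseline to day 60 between the intervention and control arms. Report the between-arm difference with its 95% CI. Cost: a wording correction in the SAP and the report, with no re-run if the interval is already available.
- **Within-arm or pooled paired test:** replace it with a between-arm analysis. The mixed model is the natural choice, since it was pre-specified and has already been run; the cost is to promote it and report its arm estimate with a 95% CI. An ANCOVA of day-60 SF-36 on arm and baseline score would also answer the question, at the cost of one analysis of existing data.

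In either case, an ANCOVA may be reported beside the mixed model, since it matches the basis of the power calculation. Any analysis changed or added now should be labelled a post-hoc correction, because the results are known. Each estimate should carry its target: average SF-36 over follow-up for the mixed model, day-60 change for the t-test. No new patients or data are needed.
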